#### 9.8.5.3.4. *Biomarkers and Pharmacodynamics*

- Determine the potential innate and acquired resistance mechanisms to DCC-2618 in GIST.
- Assess KIT/PDFGRA mutations and mutant allele frequency at baseline and the treatment effect of DCC-2618 on KIT/PDGFRA mutant allele frequency.
- Evaluate the association of anti-tumor activity/safety of DCC-2618 with the following:
  - baseline KIT/PDFGRA mutation status
  - expression of KIT protein in tumor

- expression or polymorphic variation in drug metabolic and/or drug transporter genes

## **9.8.6. Safety Analysis**

### **9.8.6.1. Adverse Events**

AEs will be summarized utilizing the number of events and proportion of patients overall, by system organ class (SOC) and preferred term for the Safety population. All tables will only include TEAEs, where treatment emergent is defined as any AE that occurs after administration of the first dose of study drug and through 30 days after the last dose of study drug, but data listings will include all collected AEs.

AE toxicity grade will be classified using NCI-CTCAE Version 5.0 criteria (See [Table 12](#)). If a patient has multiple occurrences of the same SOC or preferred term, then only the most severe event will be summarized in the tables for that SOC and preferred term. AEs of  $\geq$  Grade 3 will also be summarized. A missing toxicity grade will not be imputed.

The AE analysis will be repeated for SAEs, AEs leading to dose reduction or discontinuation, and AESIs.

No formal hypothesis-testing analysis of AE incidence rates will be performed.

### **9.8.6.2. Eastern Cooperative Oncology Group Performance Status**

Baseline, post baseline, and change at post baseline from baseline values will be summarized by time point utilizing descriptive statistics. No formal hypothesis-testing analysis will be performed.

### **9.8.6.3. Vital Signs**

Assessments will be summarized overall by time point utilizing continuous descriptive statistics. In addition, the change from baseline will be summarized for continuous parameters. For categorical parameters, the n and percentage will be displayed. No formal hypothesis-testing analysis will be performed.

### **9.8.6.4. Echocardiogram/Multigated Acquisition Scans**

Assessments will be summarized overall by time point utilizing continuous descriptive statistics. In addition, the change from baseline will be summarized for continuous parameters. For categorical parameters, the n and percentage will be displayed. No formal hypothesis-testing analysis will be performed.

### **9.8.6.5. Dermatologic Assessments**

Dermatologic assessments will be summarized by descriptive statistics. No formal hypothesis-testing analysis will be performed.

### **9.8.6.6. Clinical Laboratory Parameters**

Assessments will be summarized overall by time point utilizing continuous descriptive statistics. In addition, the change from baseline will be summarized for continuous parameters. For categorical parameters, the n and percentage will be displayed. No formal hypothesis-testing analysis will be performed.

### **9.8.7. Pharmacokinetic Analysis**

Plasma concentrations of DCC-2618 and metabolite DP-5439 will be summarized utilizing continuous descriptive statistics, according to study visit and scheduled sampling time. In the event of dose modifications, plasma concentrations may also be summarized by dose level.

[REDACTED]

### **9.8.9. Pharmacogenomic Analysis**

Pharmacogenomic analysis may be performed to explore the impact of variations in genes encoding for drug metabolism enzymes and drug transporters on patient's response to study drug.

### **9.8.10. Healthcare Utilization**

Data collected on the HCUQ (See [Appendix 17.2](#)) will be summarized using descriptive statistics as appropriate based on the item collected. These data will be compared between treatment groups over time as applicable using the appropriate statistical test.

### **9.8.11. Procedures for Reporting Deviations to Original Statistical Analysis Plan**

All deviations from the original SAP will be provided in the final clinical study report.

## **10. STUDY COMMITTEES**

### **10.1. Independent Data Monitoring Committee**

An independent data monitoring committee (IDMC) will monitor the safety and efficacy data from this study on a periodic basis to help ensure the ongoing safety of study patients. The IDMC will consist of an experienced biostatistician and two qualified clinicians, who are not employees of the Sponsor, with combined scientific expertise in general oncology and GIST and practical experience conducting clinical studies and monitoring safety and efficacy of clinical studies. The IDMC objectives and operational details will be defined in a separate document (IDMC Charter), which will be finalized before the first patient is randomized in the study.

## **11. QUALITY CONTROL AND QUALITY ASSURANCE**

### **11.1. Study Site Monitoring Visits**

During study conduct, the Sponsor or its agent will conduct periodic monitoring visits to ensure that the protocol and ICH GCPs are being followed. The monitors will review source documents to confirm that the data recorded on eCRFs is accurate. The Investigator and institution will allow the Sponsor's monitors or designees and appropriate regulatory authorities direct access to source documents to perform this verification.

The study site may be subject to review by the IRB/IEC/REB, and/or to quality assurance audits performed by the Sponsor, or companies working with or on behalf of the Sponsor, and/or to inspection by appropriate regulatory authorities.

It is important that the Investigator and their relevant personnel are available during the monitoring visits and possible audits or inspections and that sufficient time is devoted to the process.

### **11.2. Protocol Compliance**

The Investigator must conduct the study in compliance with the protocol provided by the Sponsor and given approval/favorable opinion by the IRB/IEC/REB and the appropriate regulatory authorities. Modifications to the protocol must not be made without agreement between both the Investigator and the Sponsor. Changes to the protocol will require written IRB/IEC/REB and the appropriate regulatory authority(ies) approval/favorable opinion prior to implementation, except when the modification is needed to eliminate an immediate hazard(s) to patients. The IRB/IEC/REB may provide, if applicable regulatory authority(ies) permit, expedited review and approval/favorable opinion for minor change(s) in ongoing studies that have the approval/favorable opinion of the IRB/IEC/REB. The Sponsor must ensure that all protocol modifications are submitted to the regulatory authority(ies) in accordance with the governing regulations.

If other unexpected circumstances arise that require deviation from protocol-specified procedures, the Investigator must consult with the Sponsor (and IRB, IEC, or REB, as required) to determine the appropriate course of action.

The site must document all protocol deviations in the patient's source documents. In the event of a significant deviation, the site must notify the Sponsor (and IRB, IEC, or REB, as required). Significant deviations include, but are not limited to, those that involve fraud or misconduct, increase the health risk to the patient, or confound interpretation of primary study assessments.

## **12. DATA HANDLING AND RECORD KEEPING**

### **12.1. Electronic Case Report Form**

The Sponsor or designee will provide the study sites with secure access to and training on the electronic data capture application sufficient to permit site personnel to enter or correct information in the eCRFs on the patients for which they are responsible.

An eCRF is required and must be completed for each randomized patient. The Investigator has ultimate responsibility for the accuracy, authenticity, and timely collection and reporting of all clinical, safety, and laboratory data entered on the eCRFs and any other data collection forms. Source documentation supporting the eCRF data must indicate the patient's participation in the study and must document the dates and details of study procedures, AEs, other observations, and patient status.

The Investigator, or designated representative, must complete the eCRF as soon as possible after information is collected.

The audit trail will show the user's identification information and the date and time of the any correction. The eCRFs must be signed electronically by the Investigator to attest that the data contained on the eCRFs, including any changes made to the eCRFs, is correct and endorse the final submitted data for the patients for whom the Investigator is responsible.

The completed eCRFs are the sole property of the Sponsor and must not be made available in any form to third parties, except for authorized representatives of the Sponsor or appropriate regulatory authorities, without written permission from the Sponsor.

The Sponsor will retain the eCRF data and corresponding audit trails. A copy of the final archival eCRF in the form of a compact disc or other electronic media will be provided to the site for placement in the Investigator's study file.

### **12.2. Record Retention**

To enable evaluations and/or audits from regulatory authorities or the Sponsor, the Investigator agrees to keep records, including the identity of all participating patients (sufficient information to link records, e.g. eCRFs and hospital records), all original signed ICFs, eCRFs, SAE forms, source documents, detailed records of treatment disposition, and adequate documentation of relevant correspondence (e.g. letters, meeting minutes, telephone calls reports). The records must be retained by the Investigator according to the ICH, local regulations, or as specified in the Clinical Study Agreement, whichever is longer.

If the Investigator becomes unable for any reason to continue to retain study records for the required period (e.g. retirement, relocation), the Sponsor must be prospectively notified. The study records must be transferred to a designee acceptable to the Sponsor, such as another Investigator, another institution, or to the Sponsor. The Investigator must obtain the Sponsor's written permission before disposing of any records, even if retention requirements have been met.

## **13. ETHICS**

### **13.1. Ethical Conduct of the Study**

The study will be conducted in accordance with the Declaration of Helsinki on Ethical Principles for Medical Research Involving Human Subjects, adopted by the General Assembly of the World Medical Association (28).

In addition, the study will be conducted in accordance with the protocol, ICH GCP, and applicable local regulatory requirements and laws.

The Investigator must ensure that this study is conducted in full conformity with Regulations for the Protection of Human Subjects of Research codified in 21 CFR Part 50, 21 CFR Part 54, 21 CFR Part 56, 21CFR Part 312, 21 CFR Part 314 and ICH GCP E6.

### **13.2. Patient Information and Consent**

All parties must ensure protection of patient personal data and must not include patient names on any Sponsor forms, reports, publications, or in any other disclosures, except where required by laws. In case of data transfer, the Sponsor must maintain high standards of confidentiality and protection of patient personal data.

The ICF must be in compliance with ICH GCP, local regulatory requirements, and legal requirements.

The ICF used in this study, and any changes made during the course of the study, must be prospectively approved by both the IRB/IEC/REB and the Sponsor before use.

The Investigator must ensure that each study patient is fully informed about the nature and objectives of the study and possible risks associated with participation. The Investigator, or a person designated by the Investigator, must obtain written informed consent from each patient before any study-specific activity is performed. The Investigator must retain the original of each patient's signed consent form.

### **13.3. IRB/IEC/REB**

It is the responsibility of the Investigator to have prospective approval of the study protocol, protocol amendments, ICF, and other relevant documents, (e.g. recruitment advertisements, if applicable) from the IRB/IEC/REB. All correspondence with the IRB/IEC/REB must be retained in the Investigator Site File.

The only circumstance in which an amendment may be initiated prior to IRB/IEC/REB approval is where the change is necessary to eliminate apparent immediate hazards to the patients. In that event, the Investigator must notify the IRB/IEC/REB and the Sponsor in writing immediately after the implementation.

### **13.4. Patient Confidentiality**

The Sponsor and designees affirm and uphold the principle of the patient's right to protection against invasion of privacy. Throughout this study, a patient's source data must only be linked to the Sponsor's clinical study database or documentation via a unique identification number. As permitted by all applicable laws and regulations, limited patient attributes, such as sex, age, or date of birth may be used to verify the patient and accuracy of the patient's unique identification number.

To comply with ICH GCP and to verify compliance with this protocol, the Sponsor requires the Investigator to permit its monitor or designee's monitor, representatives from any regulatory authority (e.g. FDA), the Sponsor's designated auditors, and the appropriate IRBs/IECs/REBs to review the patient's original medical records (source data or documents), including, but not limited to, any genetic/genomic data the patient might have from testing done prior to entering the study, laboratory test result reports, ECG reports, admission and discharge summaries for hospital admissions occurring during a patient's study participation, and autopsy reports. Access to a patient's original medical records requires the specific authorization of the patient as part of the informed consent process (Section 13.2).

Copies of any patient source documents that are provided to the Sponsor must have certain personally identifiable information removed (i.e. patient name, address, and other identifier fields not collected on the patient's eCRF).

### **13.5. Reporting of Safety Issues or Serious Breaches of the Protocol or International Conference on Harmonization Good Clinical Practice**

In the event of any prohibition or restriction imposed (i.e. clinical hold) by an applicable Competent Authority, or if the Investigator is aware of any new information which might influence the evaluation of the benefits and risks of the study drug, the Sponsor must be informed immediately.

In addition, the Investigator must inform the Sponsor immediately of any urgent safety measures taken by the Investigator to protect the study patients against any immediate hazard, and of any serious breaches of this protocol or of ICH GCP that comes to the attention of the Investigator.

### **13.6. Liability and Insurance**

The Sponsor has subscribed to an insurance policy covering, in its terms and provisions, its legal liability for injuries caused to participating persons and arising out of this research performed strictly in accordance with the scientific protocol as well as with applicable law and professional standards.

## **14. STUDY TERMINATION**

When the Sponsor is aware of information on matters concerning the quality, efficacy, and safety of the study drug, as well as other important information that may affect proper conduct of the clinical study, the Sponsor may discontinue the clinical study and send a written notice of the discontinuation along with the reason to the Investigator.

If an Investigator intends to discontinue participation in the study, the Investigator must immediately inform the Sponsor of the discontinuation and the reason for it.

### **14.1. Criteria for Suspension or Premature Termination of the Study**

Criteria for either temporary suspension or premature termination of the study include:

1. New information regarding the safety or efficacy of the study drug that indicates a change in the known risk/benefit profile for the compound, such that the risk/benefit is no longer acceptable for patients participating in the study.
2. Significant violation of GCP that compromises the ability to achieve the primary study objectives or compromises patient safety.
3. The Sponsor may suspend or prematurely terminate the study for reasons not related to the conduct of the study.

### **14.2. Criteria for Premature Termination or Suspension of Investigational Sites**

A study site may be terminated prematurely or suspended if the site (including the Investigator) is found to be in significant violation of GCP, protocol, contractual agreement, or is unable to ensure adequate performance of the study.

### **14.3. Procedures for Premature Termination or Suspension of the Study or the Participation of Investigational Site(s)**

In the event that the Sponsor elects to terminate or suspend the study or the participation of an investigational site, a study-specific procedure for early termination or suspension will be provided by the Sponsor. The procedure will be followed by applicable investigational sites during the course of termination or study suspension.

## 15. PUBLICATION OF STUDY RESULTS

Any and all scientific, commercial, and technical information disclosed by the Sponsor in this protocol or elsewhere must be considered the confidential and proprietary property of the Sponsor. The Investigator shall hold such information in confidence and shall not disclose the information to any third party except to such of the Investigator's employees and staff as have been made aware that the information is confidential and who are bound to treat it as such and to whom disclosure is necessary to evaluate that information. The Investigator shall not use such information for any purpose other than determining mutual interest in performing the study and, if the parties decide to proceed with the study, for the purpose of conducting the study.

The Investigator understands that the information developed from this clinical study will be used by the Sponsor in connection with the development of the study drug and therefore may be disclosed as required to other clinical investigators, business partners and associates, the FDA, and other government agencies. The Investigator also understands that, to allow for the use of the information derived from the clinical study, the Investigator has the obligation to provide the Sponsor with complete test results and all data developed in the study.

No publication or disclosure of study results will be permitted except under the terms and conditions of a separate written agreement between the Sponsor and the Investigator and/or the Investigator's institution.

## 17. APPENDICES

### 17.1. Modified Response Evaluation Criteria in Solid Tumors (mRECIST)

mRECIST criteria includes:

- No lymph nodes chosen as target lesions; enlarged lymph nodes followed as non-target lesions;
- No bone lesions chosen as target lesions;
- Positron emission tomography (PET) not acceptable for radiological evaluation;
- A progressively growing new tumor nodule within a pre-existing tumor mass must meet the following criteria to be considered as unequivocal evidence of progression according to the modification of RECIST Version 1.1: (a) the lesion is at least 2 cm in size and definitively a new active GIST lesion (e.g. enhancing with contrast or other criteria to rule out artefact); or (b) the lesion has to be expanding on at least 2 sequential imaging studies.

Source: Demetri GD, Reichardt P, Kang YK, Blay JY, Rutkowski P, Gelderblom H, Hohenberger P, Leahy M, von Mehren M, Joensuu H, Badalamenti G, Blackstein M, Le Cesne A, Schöffski P, Maki RG, Bauer S, Nguyen BB, Xu J, Nishida T, Chung J, Kappeler C, Kuss I, Laurent D, Casali PG; GRID study investigators. Efficacy and safety of regorafenib for advanced gastrointestinal stromal tumours after failure of imatinib and sunitinib (GRID): an international, multicentre, randomised, placebo-controlled, phase 3 trial. *Lancet*. 2013 Jan 26;381(9863):295-302.

## 17.2. Healthcare Utilization Questionnaire

### Healthcare Utilization Questionnaire Instructions

**Administration:** The questionnaire should be completed via a patient interview by a healthcare provider participating in the study.

### Healthcare Utilization Questionnaire

#### A. Healthcare Visits

Other than what was required for this study, did you use any of the following health care services during the last 28 days (4 weeks)?	Yes	No	Number during the last 28 days
Emergency room visit			
Use of an ambulance			
Outpatient primary care physician visit			
Outpatient specialist visit (e.g., oncologist, surgeon)			
Outpatient counseling visit (e.g., psychiatrist, psychologist, therapist, mental health specialist)			
Other			

#### B. Inpatient Visits

Did you spend any days in the following facilities during the last 28 days (4 weeks)?	Yes	No	Length of Stay (days)	Reason for Stay
Inpatient hospital				 Disease/treatment related  Other
Rehabilitation facility				 Disease/treatment related  Other
Hospice facility				 Disease/treatment related  Other
Respite care (eg, caregiver relief)				 Disease/treatment related  Other
Skilled nursing facility/nursing home				 Disease/treatment related  Other

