## **6.15. Healthcare Utilization**

### **6.15.1. Healthcare Utilization Questionnaire (HCUQ)**

The Healthcare Utilization Questionnaire (HCUQ) [See [Appendix 17.2](#)] was designed specifically to collect data on the use of healthcare resources. It will be completed via a patient interview conducted by the Investigator or designee participating in this study at the visits indicated in [Table 1](#) (schedule of assessments). The required time for completion is approximately 3-5 minutes.

The first section of the questionnaire deals with utilization of ambulatory healthcare services, with the staff member asking the patient about utilization of each of the services (emergency room, ambulance, primary care physician, specialist physician, counseling, other) and recording information as to whether the type of service had been used in the past 28 days (yes, no) and, if so, the number of times it was utilized. The second section proceeds in a similar way with data collection regarding the number of hospital admissions in the past 28 days, the length of stay, and the reason for each admission (disease/treatment related, other). The last section focuses on paid care provided in the patient's home by a nurse, home health aide, hospice worker, or another provider type in the last 28 days, with collection of whether service was provided and, if so, the number of days and the number of hours per day.

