## 7.8. Serious Adverse Events

An AE is considered serious if it meets any of the following:

- Results in death (regardless of cause, that occurs during participation in the study or occurs after participation in the study and is suspected of being a delayed toxicity due to administration of the study drug)
- Is life threatening (an event/reaction in which the patient was at risk of death at the time of the event/reaction; it does not refer to an event/reaction which hypothetically might have caused death if it were more severe)
- Requires inpatient hospitalization or prolongation of existing hospitalization
- Results in persistent or significant disability/incapacity
- Results in congenital anomaly/birth defect
- Important medical events that may not result in death, are life-threatening, or require hospitalization may be considered serious when, based upon appropriate medical judgment, they may jeopardize the patient and may require medical or surgical intervention to prevent one of the outcomes (i.e. allergic bronchospasm requiring intensive treatment in an emergency room or at home, blood dyscrasias or convulsions that do not result in inpatient hospitalization, or the development of drug dependency or drug abuse).

Clinical outcomes or symptoms related to progressive disease need to be reported as an SAE if they meet SAE criteria and occur within 30 days of the last dose of study drug. They must be reported according to the diagnosis or symptom of event and not by the term "progressive disease."

Clarification must be made between the terms "serious" and "severe," because they are not synonymous. The term "severe" is often used to describe the intensity (severity) of a specific event, as in mild, moderate, or severe myocardial infarction. The event itself, however, may be of relatively minor medical significance, such as a severe headache. This is not the same as "serious," which is based on patient/event outcome or action criteria described above and is usually associated with events that pose a threat to a patient's life or functioning. Seriousness, not severity, serves as a guide for defining regulatory reporting obligations.

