### 9.2.3.3. Healthcare Utilization

- Changes over time in healthcare utilization

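### The inpatient part of the healthcare-utilization form has no count of stays and only one length and one reason per facility type, so it cannot supply the admission count that Protocol Section 6.15.1 says it collects

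*Protocol*

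**What the plan says.** Healthcare utilization is an exploratory objective (Protocol Section 2.3; SAP Section 2.1.4). The endpoint in Protocol Section 9.2.3.3 is "Changes over time in healthcare utilization".

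Protocol Section 6.15.1 explains the questionnaire. Its first part asks about ambulatory services and how often each was used. Its second part is said to follow the same pattern, and its content is given as "data collection regarding the number of hospital admissions in the past 28 days, the length of stay, and the reason for each admission".

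The form is printed in Protocol Appendix 17.2. Part A, on healthcare visits, has a column headed "Number during the last 28 days". Part B, on inpatient visits, opens with "Did you spend any days in the following facilities during the last 28 days (4 weeks" and has four answer columns: yes, no, one for length of stay in days, and "Reason for Stay". There is one row for each of five facility types: inpatient hospital, rehabilitation, hospice, respite care and skilled nursing.

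For the analysis, Protocol Section 9.8.10 plans descriptive statistics suited to each item collected and adds: "These data will be compared between treatment groups over time as applicable using the appropriate statistical test". The SAP lists the objective but sets out no analysis of the questionnaire and no derivation of admissions.

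**The concern.** The protocol text and the form disagree about what is recorded. The text promises a count of admissions and a reason for each one. The form records whether there was any stay, with one length and one reason per facility type. Two hospital stays within the 28-day recall period share one row. If one was related to the disease or its treatment and the other was not, the days cannot be divided between the two reasons.

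What is at stake is whether the trial can report admissions as the protocol describes them. An item that was never asked for cannot be summarized or compared later, and a count not taken within the recall period may be hard to reconstruct.

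**Working it through.** The plan gives no figure to reproduce. The check sets the description against the form, item by item.

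| Item described in Section 6.15.1 | Field in Part B of the form | What can be obtained |
|---|---|---|
| Number of admissions in 28 days | None | Any stay or none, per facility type |
| Length of stay | One cell per facility type | Total days, if that is what is entered; the form does not say |
| Reason for each admission | One pair of check boxes per facility type | The reason, if there was exactly one stay; otherwise no link between reason and stay |

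1. **Count.** A yes means one or more stays. The count is unavailable for every patient with a stay, because the form does not show which patients had exactly one.

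2. **Length.** Take one patient with a single 6-day hospital stay and another with two 3-day stays for the same reason. If totals are entered, the second patient's entry is 3 + 3 = 6 days, and both records read yes, 6 days. If a site enters one stay only, the second record reads yes, 3 days. The form does not define the entry, so sites may differ.

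3. **Reason.** Even if both boxes are ticked, the form does not show how many stays or days belong to each reason.

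4. **Is a column missing only because of how the text was extracted?** This is unlikely. The Part B header and its five rows share one consistent structure. Part A keeps its count column, and Part C keeps its columns for days and for hours per day.

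5. **Does another section supply the count?** Section 9.8.10 works from the items collected, and the SAP adds no derivation. Serious adverse event reporting is a partial source, considered with the opposing case, but no section plans to use it for this endpoint.

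**The case against.** The strongest reply is that admissions are recorded elsewhere. Protocol Section 7.8 makes an adverse event serious if it "Requires inpatient hospitalization or prolongation of existing hospitalization", and it also requires clinical outcomes or symptoms of progression that meet a seriousness criterion within 30 days of the last dose to be reported. Under Sections 7.10 and 7.11 such events are reported regardless of causality, from consent to 30 days after the last dose (ending earlier if new anticancer therapy starts). A reader might infer that repeat admissions for toxicity or progression are lost to the trial. The documents do not support that: many of them should be captured as individual events.

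This narrows the point but does not remove it. Planned admissions for illness that existed before screening are generally not adverse events (Section 7.1). The criterion concerns inpatient hospitalization, so it does not by itself cover the other four facility types. No section links these records to the questionnaire.

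A second reply is that useful comparisons remain, and this stands. A reader might infer that the arms can be compared only on whether patients had any stay. The form also collects days and reason by facility type, and Section 9.8.10 allows those to be compared.

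A third reply is that a count field would still leave admissions incomplete. The questionnaire is given on Day 1 of each 42-day cycle and at end of treatment but looks back only 28 days, so between consecutive Day 1 visits 42 − 28 = 14 days (14/42 = 33%) are not covered, taking visits as on schedule. This is correct. It limits what the fix can achieve but does not excuse the mismatch between text and form.

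**Conclusion.** The inconsistency is real and minor. The number of admissions cannot be obtained from the form, and length and reason cannot be tied to individual stays when a patient has more than one in a facility type. Any stay (yes/no) remains comparable between arms, as do days per facility type provided totals are entered.

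The effect is limited to an exploratory endpoint outside the hierarchical testing sequence. The primary analysis, power and type I error are untouched.

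No percentage of undercounting should be stated. A reader might assume a readmission share and conclude that admissions are understated by that much. The documents give no such share, and no planned analysis counts each yes as one admission. The accurate statement is that the count is not collected. Nor do the documents rank admissions by cost against other resources, and the point does not depend on such a ranking.

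The conclusion assumes that the form printed in Appendix 17.2 is the one in use. The electronic case report form is not among the documents; if it already holds a count, only the printed appendix needs correcting.

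**What to change.** In Part B of the form:

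- Add a field for the number of stays during the last 28 days, as Part A has for visits.
- Define length of stay as total days in that facility type over the 28 days.
- Let the reason be recorded per stay, or as the number of stays for each of the two reasons. The second option is lighter, since the two numbers add up to the count. It gives stays by reason but not days by reason.

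No extra visit is needed, because the interview already takes place on Day 1 of each cycle and at end of treatment. A count is one added field. Length and reason for each stay would need a repeating record, which is more than one field. The documents do not allow the build cost to be checked.

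If the form can no longer be changed, correct Section 6.15.1 so that it describes what Part B records, and state how length of stay is to be read. That costs a wording change only, but it gives up the admission count.
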